Title:

The Effect of Constant 5% Versus Gradient (8%, 5%, and 2%) Oxygen Concentration on Development of Human Embryos to the Blastocyst Stage: A Sibling Oocyte Study

Study Type:

Prospective, Quasi-Randomized Sibling-Split Oocyte Study

Study Site:

Department of Reproductive Medicine and Gynecological Endocrinology

University Medical Centre Maribor

Slovenia

Clinical Trial Registration Number:

NCT05898178

Document Date:

April 24, 2025

Principal Investigator:

[name] [name]

[contact]

2. Study Design and Participants

Prospective sibling-split oocyte study , conducted at the University Medical Centre Maribor and included a total of 658 cumulus–oocyte complexes (COCs) collected from 44 ICSI cycles between January 2022 and January 2023. A quasi-randomisation into control and intervention groups was performed immediately after oocyte retrieval. Embryonic outcomes between different oxygen culture conditions were compared.

Eligibility Criteria

- Inclusion: Women <35 years old, BMI 18–30 kg/m², normal uterine cavity, ≥6 MII oocytes retrieved, first or second ICSI cycle, male factor infertility (non-azoospermic), blastocyst culture, GnRH antagonist protocol.
- **Exclusion**: Endometriosis, previous ovarian surgery, endocrine/metabolic disorders, PCOS.

Ethical Approval

- Institutional Ethics Committee of the University Medical Centre Maribor (No: UKC-MB-KME-1/21)
- National Medical Ethics Committee (No: 0120-405/2021/4)

All participants provided informed consent.

3. Objectives

Primary Objective

To compare the proportion of injected MII oocytes that developed into morphologically optimal blastocysts on day 5 between the control and intervention oxygen conditions.

Secondary Objectives

- Assessment of morphokinetic parameters (timing to key developmental stages)
- Incidence of abnormal cleavage patterns
- Morphometric characteristics of blastocysts (e.g., area, TE cell count)

4. Sample Size Determination

Sample size was calculated using the Sealed Envelope online tool (accessed January 2022). Based on a baseline blastocyst formation rate of 15% and a hypothesized improvement to 25% in the intervention group, 496 embryos (248/group) were required for 80% power at α = 0.05. With a buffer for potential fertilization failures, 47 patients were targeted. Ultimately, 44 patients were enrolled, contributing 521 injected sibling MII oocytes.

5. Randomization and Blinding

A quasi-random allocation method was used post-oocyte retrieval. Group A (control) was cultured under 5% O_2 ; Group B (intervention) under a decreasing gradient from 8% to 2% O_2 . Embryologists remained blinded through a coded system.

6. Laboratory Procedures

Sibling oocytes from each patient were divided into two groups:

- Intervention Group (8–5–2% O₂): Cultured under a dynamic oxygen gradient to mimic *in vivo* conditions. Gas levels were adjusted by stage:
 - Day 0–3: 6% CO₂, 8% O₂, and 86% N₂
 - $_{\odot}$ Day 3: Oxygen concentration was reduced to 5% (6% CO₂, 5% O₂, 89% N₂).
 - o Day 3–5: Oxygen was further reduced to 2% (6% CO_2 , 2% O_2 , 92% N_2).
- Control Group $(5\% O_2)$: Cultured under fixed conditions $(6\% CO_2, 5\% O_2)$ throughout.

Common lab procedures for both groups:

Sperm prep: Density gradient centrifugation

ICSI: Standard protocol using a Nikon Eclipse TE 2000 microscope (200x magnification).

Embryo culture: G-1 PLUS (Day 1–3) and G-2 PLUS (Day 3–5) (Vitrolife, Gothenburg, Sweden).

Monitoring: Continuous time-lapse imaging with Primo Vision system (Vitrolife, Gothenburg, Sweden).

8. Statistical Analysis Plan (SAP)

Statistical analysis was performed using SPSS (SPSS Inc., Chicago, Illinois, USA). Continuous variables were tested for normality using the Shapiro-Wilk test. Data are presented as mean \pm standard deviation (SD) for normally distributed variables or as median with interquartile range (IQR) for non-normally distributed variables. Categorical data are expressed as frequencies and percentages. Group comparisons for embryological outcomes, irregular cleavage events, and clinical outcomes were carried out using the chi-square test or Fisher's exact test, depending on the expected frequencies. Odds ratios (ORs) with 95% confidence intervals (CIs) were calculated using the Baptista-Pike method for categorical variables. Morphokinetic variables were reported as median hours post-insemination (HPI) with IQR. Differences in morphokinetic timings between oxygen groups were analyzed using a linear mixed-effects model (REML), and Šídák's correction was applied for multiple comparisons at individual time points. Morphometric measurements of blastocysts graded Gardner \geq 3 were compared using unpaired t-tests, with significance determined at p < 0.05. All statistical tests were two-sided; a p-value < 0.05 was considered statistically significant throughout the study.

10. Ethical Evaluation of the Submitted Research

10.1 Original (Slovenian language):

[name] T: [name], [name] F: [name] E: [contact], [contact] www.mz.gov.si Številka: 0120-405/2021/4 Datum: 28. 9. 2021

Zadeva: Ocena etičnosti predložene raziskave Zveza: Vaša vloga z dne 31. 8. 2021

Spoštovani,

Komisija Republike Slovenije za medicinsko etiko (v nadaljevanju KME RS) je dne 31. 8. 2021 prejela vlogo za oceno etičnosti raziskave z naslovom

"Vpliv različnih koncentracij kisika na presnovo in razvoj človeških zarodkov in vitro in nauspešnost programa oploditve z biomedicinsko pomočjo"

Gre za: fiziološko – klinično raziskavo, ki bo potekala na Oddelku za reproduktivno medicino in ginekološko endokrinologijo, Klinike za ginekologijo in perinatologijo, Univerzitetnega kliničnega centra Maribor.

Namen raziskave je določiti optimalno koncentracijo kisika in čim bolj posnemati fiziološke pogoje v kulturah človeških zarodkov ter posledično izboljšati uspeh programa oploditve z biomedicinsko pomočjo (OBMP).

Spremljali bi fiziološki vpliv kisika na nivo optimalne blastulacije zarodkov, ki je trenutno 10% pri uporabljenem 5 % kisiku v atmosferi inkubatorjev. Ob hipotezi, da gojenje zarodkov pri atmosferi z 2 % izboljša optimalno blastulacijo zarodkov na 20 %, bi potrebovali skupno 398 zarodkov. Pri tem upoštevate statistično moč 80 % in a = 0,05. V raziskavo bi torej vključili največ 100 preiskovanih parov (ciklusov OBMP z vsaj 4 jajčnimi celicami). Povprečno minimalno število jajčnih celic na pacienta v Mariborski IVF enoti, je okoli 8 jajčnih celic (6 zrelih M II jajčnih celic). Stopnja oploditve po ICSI je okoli 70 %. To pomeni da boste v raziskavi razpolagali s približno 400 zarodki. Vsaka raziskovalna skupini bo vsebovala 200 zarodkov.

KME RS je na seji 21. septembra 2021 obravnavala prejeto vlogo in ugotovila, da je vloga popolna ter ocenila, da je raziskava etično sprejemljiva. S tem vam za njeno izvedbo izdaja svoje soglasje.

[name], mag. biol. in ekol. Oddelek za reproduktivno medicino in ginekološko endokrinologijo Klinika za ginekologijo in perinatologijo UKC Maribor [name]

e-naslov: [contact]

Pri nadaljnjih dopisih v zvezi z raziskavo se obvezno sklicujte na številko tega dopisa.

S spoštovanjem,

dr. [name], dr. med. predsednik KME RS

Vročiti: – naslovniku – po e-pošti

10.2 Translation (English language):

Republic of Slovenia Ministry of Health [name] T: [contact], [contact] F: [contact] E: [contact], [contact] www.mz.gov.si

Reference No.: 0120-405/2021/4 Date: September 28, 2021

Subject: Ethical Evaluation of the Submitted Research Reference: Your application dated August 31, 2021

Dear Sir/Madam,

The National Medical Ethics Committee of the Republic of Slovenia (hereinafter: NMEC RS) received your application on August 31, 2021, for the ethical assessment of the research titled

"The Effect of Different Oxygen Concentrations on the Metabolism and Development of Human Embryos In Vitro and on the sucess of assisted reproductive technology (ART) programs."

This is a physiological-clinical study, which will be conducted at the Department of Reproductive Medicine and Gynecological Endocrinology, Clinic for Gynecology and Perinatology, University Medical Centre Maribor.

The purpose of the research is to determine the optimal oxygen concentration and to best simulate physiological conditions in human embryo cultures, thereby improving the success of medically assisted reproduction (MAR) programs.

The study will observe the physiological impact of oxygen on the level of optimal blastulation of embryos, currently at 10% under a 5% oxygen atmosphere in incubators. Based on the hypothesis that culturing embryos at 2% oxygen may improve optimal blastulation to 20%, a total of 398 embryos would be required. This calculation assumes a statistical power of 80% and α = 0.05. Accordingly, a maximum of 100 participating couples (MAR cycles with at least four oocytes each) would be included in the study. The average minimum number of oocytes per patient at the Maribor IVF unit is about 8 oocytes (6 mature MII oocytes). The fertilization rate following ICSI is around 70%. Therefore, the study is expected to involve approximately 400 embryos, with 200 embryos per research group.

At its meeting on September 21, 2021, the NMEC RS reviewed the application, found it to be complete, and assessed the study as ethically acceptable. Therefore, the Committee grants its approval for the study to be conducted.

Sincerely,

[name], M.D. Chair, National Medical Ethics Committee of the Republic of Slovenia Delivered to: - Recipient via e-mail

Contact:

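### Does quasi-random allocation at retrieval, with a primary proportion per injected MII oocyte, call for an as-allocated analysis?

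*Combined protocol and SAP*

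**What the plan says.** All references are to the Combined protocol and SAP. Section 2 (Study Design and Participants) says "A quasi-randomisation into control and intervention groups was performed immediately after oocyte retrieval", and counts the study material as 658 COCs from 44 cycles. Section 5 (Randomization and Blinding) repeats that "A quasi-random allocation method was used post-oocyte retrieval" and adds "Embryologists remained blinded through a coded system". Section 6 (Laboratory Procedures) says only "Sibling oocytes from each patient were divided into two groups", without specifying COCs or mature oocytes. It lists the arm-specific gas from Day 0.

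The eligibility criteria in section 2 require "≥6 MII oocytes retrieved". The primary objective in section 3 is "To compare the proportion of injected MII oocytes that developed into morphologically optimal blastocysts on day 5". Section 4 (Sample Size Determination) closes with "Ultimately, 44 patients were enrolled, contributing 521 injected sibling MII oocytes". Section 8 (Statistical Analysis Plan) states "Group comparisons for embryological outcomes, irregular cleavage events, and clinical outcomes were carried out using the chi-square test", with Fisher's exact test as the alternative. It names no analysis set and no analysis by allocated COC. Sections 7 and 9 are not in the text available, so absence can be claimed only for what is there.

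**The concern.** If COCs were assigned to an oxygen condition at retrieval and only injected MII oocytes were counted, about one allocated unit in five left the denominator after assignment. Exclusions after allocation can undo comparability, above all when the allocation was quasi-random and its rule is not given. If the fraction injected differed between arms, part of any difference in optimal blastocysts could come from which oocytes entered each denominator rather than from the oxygen regimen.

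The totals 658 and 521 are not split by arm, so a reader cannot check this. The text also does not say whether the arm-specific gas began before injection. If it did, being an injected MII oocyte would itself be observed after exposure. A table of counts by arm and a sensitivity analysis per allocated COC would be the natural requests.

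**Working it through.** **Inputs.** Section 2: 658 COCs, 44 cycles. Section 4: 521 injected MII oocytes; 15% versus 25%; 248 per group, 496 in total; 80% power; α = 0.05. Section 8: two-sided tests. Section 10.2 (ethics letter, English translation): about 8 oocytes per patient, 6 of them mature. Assumed, because no by-arm counts are given: 329 COCs per arm (658/2). Oocytes are treated as independent.

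**1. The plan's own figure.** With (z₀.₉₇₅ + z₀.₈₀)² = 7.849, n per group = 7.849 × (0.15 × 0.85 + 0.25 × 0.75) / 0.10² = 7.849 × 0.315 / 0.01 = 247.2. This rounds up to 248, and 2 × 248 = 496. The stated sample size is reproduced, and the present point does not affect it.

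**2. The gap.** 658 − 521 = 137; 137/658 = 20.8%; 137/44 = 3.1 per patient.

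**3. Is the gap unusual for this unit?** The ethics letter implies (8 − 6)/8 = 25% not mature. Applied to 658 COCs, that is 164.5 oocytes, and the observed gap of 137 is smaller. It looks like ordinary attrition for maturity, although the reasons for non-injection are not given.

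**4. How unequal could losses be by chance?** If 137 losses fall at random on two arms of 329, the count in one arm is hypergeometric. The mean is 68.5. The variance is 329 × (137/658) × (521/658) × (329/657) = 27.2, so the SD is 5.2 and the 95% range is about 58 to 79.

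**5. Effect on the primary difference, no true effect.** Hold 0.15 × 260.5 ≈ 39 optimal blastocysts in each arm and let only the denominators move. This gives the additional injected oocytes no potential at all.

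| Losses | Injected | Rates | Difference |
|---|---|---|---|
| 68.5 / 68.5 | 260.5 / 260.5 | 15.0% / 15.0% | 0 |
| 77 / 60 | 252 / 269 | 15.5% / 14.5% | 1.0 point |
| 79 / 58 | 250 / 271 | 15.6% / 14.4% | 1.2 points |
| 97 / 40 | 232 / 289 | 16.8% / 13.5% | 3.3 points |
| 117 / 20 | 212 / 309 | 18.4% / 12.6% | 5.8 points |

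The last two rows lie (68.5 − 40)/5.2 = 5.5 and (68.5 − 20)/5.2 = 9.3 SDs from balance. They would need a systematic cause, and the documents show none.

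**6. Same imbalance, ordinary potential.** With 252 and 269 injected, each at 15%, the expected blastocysts are 37.8 and 40.4. The rate per injected oocyte is 15% in both arms, so the difference is 0. The rate per COC is 37.8/329 = 11.5% versus 40.4/329 = 12.3%, a gap of 0.8 points. Here the proposed sensitivity analysis is the one that misleads.

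**7. What an analysis per COC would offer.** The planning rates become 0.792 × 15% = 11.9% and 0.792 × 25% = 19.8%. Power is about 80% with 329 per arm, against about 82% per injected oocyte with 260.5 per arm. The loss of power is small, but step 6 shows that this denominator is not free of bias either.

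**The case for a change.** The best case for acting is that timing at retrieval, together with a count of material in COCs, favours COCs as the allocated unit. If that is right and the gas differed from Day 0 before injection, the primary denominator is conditioned on something that happened after exposure. The quasi-random rule is undisclosed, so balance should be shown and not presumed. The stated blinding is not said to cover allocation or the choice of oocytes to inject. One table and one supportive analysis would cost little.

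Part of this stands. The rule, the unit, and the timing relative to the maturity check and the gas exposure are not stated, and a reader would want them. But the inference to COCs is not secure: the eligibility threshold is a count of mature oocytes, section 6 speaks only of sibling oocytes, and section 4 describes the 521 as sibling MII oocytes. If mature oocytes were divided, no loss arises from this source.

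The remedy also misses its target. The characteristic risk of a quasi-random rule is predictability, which could let better oocytes go to one arm. Counts can balance while quality differs, and a rate per COC inherits the same steering. The extra analysis needs the arm of non-injected COCs to have been recorded, which the text does not say. It also brings in oocytes outside the stated objective. Counts by arm are results and belong in the report. Allowing for patient in the analysis is a separate question.

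**Conclusion.** The quotations and the arithmetic behind the concern are correct, but no stated rule or figure is shown to give a wrong result. The 20.8% is a post-allocation loss only under one reading of the text, and it agrees with the unit's own planning figure of about 25% not mature. Under an assumed 329 COCs per arm and no true effect, chance imbalance shifts the primary difference by 0 to about 1.2 points against the planned 10. That shift is sampling variation rather than bias.

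The denominator of injected oocytes matches the stated objective and keeps fertilisation failures in. The split within each patient and the stated blinding lower the risk further. The quasi-random nature of the allocation is a real limitation, but the study type line and sections 2 and 5 already disclose it, and collection ended in January 2023. What remains is descriptive detail that the authors would sensibly supply when reporting: the rule, the unit, the timing, and counts by arm with reasons for non-injection. An analysis per COC is optional and at most supportive. The primary analysis is unchanged in either case. This conclusion would need another look if the counts by arm proved far outside the chance range of 58 to 79 losses.

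### The primary comparison treats 521 sibling oocytes from 44 women as independent, so its p-value and confidence interval do not fit the split design

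*Combined protocol and SAP*

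**What the plan says.** Section 6 (Laboratory Procedures) sets out the split: "Sibling oocytes from each patient were divided into two groups". Every woman therefore contributes to both arms. The primary objective in section 3 is "To compare the proportion of injected MII oocytes that developed into morphologically optimal blastocysts on day 5", so the unit of analysis is the oocyte. Section 4 gives the numbers: "Ultimately, 44 patients were enrolled, contributing 521 injected sibling MII oocytes".

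Section 8 (SAP) states: "Group comparisons for embryological outcomes, irregular cleavage events, and clinical outcomes were carried out using the chi-square test", or Fisher's exact test, the choice depending on expected counts. It adds: "Odds ratios (ORs) with 95% confidence intervals (CIs) were calculated using the Baptista-Pike method for categorical variables". The SAP names no separate test for the primary endpoint, but that endpoint is a binary embryological outcome and no other sentence covers it. No pairing, stratification by woman, random effect, GEE or robust variance appears for any binary outcome. A linear mixed model is named for morphokinetic timings only, and its random effects are not specified.

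**The concern.** A chi-square or Fisher test on one 2x2 table, and a Baptista-Pike interval from the same table, assume that all oocytes are independent and that the arms are unrelated samples. Here each woman supplies on average 521/44 = 11.8 oocytes, about half to each arm.

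Two kinds of correlation matter, and they act in opposite directions. A woman effect shared by both arms cancels in the arm difference. Ignoring it makes the standard error too large and discards the precision that a sibling split is meant to give. Variation specific to one woman in one arm (a shared dish or incubator, or an individual response to oxygen) does not cancel. Ignoring that makes the standard error too small.

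The familiar rule that ignoring clustering always makes p-values too small therefore does not apply automatically here. What is at stake is whether the p-value and interval for the trial's single primary question have their stated properties.

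**Working it through.** **Inputs from the documents.** 44 women and 521 injected oocytes (section 4); 15% versus 25%, 80% power, alpha 0.05, 248 per group (section 4); two-sided tests (section 8). An even split within each woman is taken from the equal group sizes, giving m = 521/88 = 5.92 oocytes per woman per arm. No intra-woman correlation is given, so the values below are assumed.

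**Step 1: the plan's own figure.** With independent proportions and unpooled variance,

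n = (1.960 + 0.842)² × (0.15 × 0.85 + 0.25 × 0.75) / 0.10² = 7.85 × 0.315 / 0.01, which rounds up to 248 per group, 496 in total.

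This matches section 4 exactly, so independence is built into the sample size as well as the analysis.

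**Step 2: variance under the split design.** Let ρw be the correlation between two oocytes of one woman in the same arm, and ρb the correlation between two in opposite arms. Relative to the independence variance, the variance of the arm difference is

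DE = 1 + (m − 1)ρw − mρb.

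The true type I error of the unadjusted test is 2 × [1 − Φ(1.96/√DE)].

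| ρw | ρb | DE | True type I error |
|---|---|---|---|
| 0.05 | 0.05 | 0.95 | 0.044 |
| 0.10 | 0.10 | 0.90 | 0.039 |
| 0.20 | 0.20 | 0.80 | 0.028 |
| 0.30 | 0.30 | 0.70 | 0.019 |
| 0.05 | 0.025 | 1.10 | 0.061 |
| 0.10 | 0.05 | 1.20 | 0.073 |
| 0.20 | 0.10 | 1.39 | 0.097 |
| 0.30 | 0.15 | 1.59 | 0.120 |
| 0.10 | 0 | 1.49 | 0.109 |

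Worked example, ρw = 0.10 and ρb = 0.05: DE = 1 + 4.92 × 0.10 − 5.92 × 0.05 = 1.196; 1.96/√1.196 = 1.79; type I error 0.073.

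The test turns from conservative to liberal when mρb < (m − 1)ρw, that is when ρb falls below 4.92/5.92 = 0.83 of ρw.

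**Step 3: power of a correctly sized analysis.** With 260.5 oocytes per arm, power = Φ[(0.10 − 1.96 × se0 × √DE) / (se1 × √DE)], where se0 = √(2 × 0.20 × 0.80/260.5) = 0.0350 and se1 = √(0.315/260.5) = 0.0348. Independence gives 81.6%. For (ρw, ρb) = (0.10, 0.10), (0.10, 0.05) and (0.10, 0), power is 85.4%, 74.3% and 64.8%.

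**Step 4: simulation.** Setting: 44 women, about 521 oocytes, and woman and woman-by-arm effects on the log-odds scale.

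- No clustering: chi-square type I error 0.051.
- Shared woman effect only: 0.024 to 0.046, lower as the woman effect grows. At a woman SD of 1.5, chi-square power was 0.86 against 0.89 for a patient-clustered robust test. In separate runs at that SD it was 0.849 against 0.909 for a patient-stratified test.
- Woman-by-arm effects added, per-arm SD 0.3 to 1.0: 0.043 to 0.114 in one set of runs. Another set reached 0.130 within the range 0.7 to 1.0.
- Patient-clustered robust test: 0.035 to 0.053 over all scenarios and runs. A paired woman-level t-test stayed at 0.046 to 0.051.
- Stratifying by woman alone: 0.10 to 0.15 when woman-by-arm variation was present (per-arm SD 0.7 to 1.0).

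**The case against.** The strongest reply is that the stated test may do little harm. With a shared woman effect only, its type I error stays below 0.05 and its interval is too wide rather than too narrow, so a positive result would not be undermined. Clear inflation needs large woman-by-arm variation. A log-odds-ratio SD of 1.0 around the planned odds ratio of (0.25/0.75)/(0.15/0.85) = 1.89 implies that 95% of women's true odds ratios lie between 0.27 and 13.4. At a log-odds-ratio SD of 0.3 to 0.5, simulated type I error is 0.041 to 0.061; taken as a per-arm SD, the same values give 0.044 to 0.072. The narrow eligibility criteria may also limit variation between women, and the documents do not describe dish or incubator sharing.

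Much of this stands. Size and direction cannot be determined from the documents, and moderate heterogeneity leaves the test near nominal or mildly liberal. It is also fair that the morphokinetic mixed model is weak evidence that patient clustering was considered, since its random effects are unstated, and that changing the primary test now is post hoc.

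None of it justifies the stated test. The error vanishes only if the correlations are zero or the two terms happen to cancel, and the plan argues for neither. In the conservative case the cost is lost power and a higher risk of missing a real effect.

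**Conclusion.** The concern holds. The unadjusted chi-square or Fisher test and the Baptista-Pike interval do not match a design in which each woman contributes to both arms, and the plan contains no other analysis of the primary endpoint.

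Over the assumed correlations tabulated above, the true type I error of the nominal 5% test runs from about 0.019 (shared woman effect, ρ = 0.30) to 0.12 (ρw = 0.30, ρb = 0.15). In the first case the 5% ceiling is respected but precision is lost; in the second the interval is too narrow. These figures rest on assumed correlations and an even split within each woman. The mismatch itself does not depend on them. Because it affects the p-value and interval of the only primary question, and a method that is robust in both directions is readily available, it must be corrected.

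**What to change.** Replace the chi-square/Fisher test and Baptista-Pike odds ratio, for the primary endpoint and all other binary outcomes per oocyte or embryo, with a logistic GEE:

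- patient as the cluster and oxygen group as the covariate;
- a stated working correlation;
- robust standard errors with a small-sample correction for 44 clusters;
- odds ratio and risk difference, each with a 95% confidence interval.

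As a sensitivity analysis, fit a mixed logistic model with a patient intercept **and** a patient-by-arm term. An intercept alone does not cover the situation in which the type I error is inflated. A paired woman-level comparison is an acceptable alternative. The chi-square result can remain as a descriptive figure. The unpaired t-tests for blastocyst morphometry have the same defect and need a patient-aware counterpart.

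The document is dated April 2025 and describes cycles completed by January 2023, so the change should be labelled post hoc and the stated analysis shown beside it. The cost is SAP wording and a re-run. No new data are needed, provided that each oocyte's record is still linked to its patient, which the sibling split implies but the documents do not state. The interval may widen if woman-by-arm variation is present and narrow if it is not.

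### Šídák's correction for the embryo timings is valid but conservative; step-down Holm-Šídák would recover some power with the same family-wise control

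*Combined protocol and SAP*

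**What the plan says.** Section 3 makes timing a secondary objective: "Assessment of morphokinetic parameters (timing to key developmental stages". Section 6 follows the embryos by time-lapse: "Continuous time-lapse imaging with Primo Vision system".

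Section 8 sets the scale ("Morphokinetic variables were reported as median hours post-insemination (HPI) with IQR"), the model ("Differences in morphokinetic timings between oxygen groups were analyzed using a linear mixed-effects model (REML") and the multiplicity rule (a Šídák "correction was applied for multiple comparisons at individual time points"). The general level is given as: "All statistical tests were two-sided; a p-value < 0.05 was considered statistically significant throughout the study".

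Section 8 does not say:
- which stages, or how many, form the family;
- whether the Šídák procedure is single-step or step-down;
- what random effects or covariance structure the mixed model has.

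No power is stated for the timings. The only sample-size calculation, in Section 4, concerns the binary blastocyst endpoint.

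**The concern.** The Šídák threshold gives exactly 5% family-wise error only when the tests are independent. Here every timing is counted from the same insemination in the same embryos, so a later time contains all the earlier ones and the stage statistics are positively correlated. Under that dependence the single-step rule is stricter than its stated level requires.

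At stake is the reading of non-significant stages. Section 2 reports that the cycles ran from January 2022 to January 2023, and Section 4 reports 44 patients against a target of 47. The data set is fixed, so the efficiency of the analysis is the one thing that can still change. A real timing shift could be reported as no difference because the test is run below its nominal level.

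**Working it through.** **The plan's own figure.** For 15% against 25%, two-sided 0.05 and 80% power, the unpooled formula gives (1.960 + 0.842)² × (0.15×0.85 + 0.25×0.75) / 0.10² = 7.85 × 0.315 / 0.01 = 247.2, so 248 per group and 496 in total. This agrees with Section 4. It concerns the primary endpoint only and says nothing about power for the timings.

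**Inputs from Section 8.** Two-sided 0.05; Šídák's correction; a common time origin.

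**Assumptions, because the documents are silent.** K = 8, 12 or 15 stages; jointly normal stage statistics with correct standard errors; a shift of 3.0 SE at each affected stage.

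**Correlation.** If stage durations are independent with equal variance, cumulative times at stages i < j correlate as √(i/j). First against last is then √(1/8) = 0.35 for 8 stages and √(1/15) = 0.26 for 15; the average over all pairs is about 0.68. If fewer embryos reach later stages, the correlation of the test statistics is multiplied by √(n_j/n_i). The attrition case assumes a linear fall to 30% of embryos by the last stage.

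**Thresholds.** Single-step Šídák tests each stage at 1 − 0.95^(1/K). Max-T uses the 95% point of the largest |Z| under the assumed correlation. Power per shifted stage is Φ(3.0 − critical value); for Šídák with K = 8 it is Φ(3.0 − 2.727) = 61%. The max-T points, the true family-wise error of Šídák and the Holm-Šídák power come from 200,000 simulated draws per case.

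| K | Šídák per-test α | Šídák z | Correlation | True family-wise error of Šídák | Max-T point | Power, Šídák | Power, max-T |
|---|---|---|---|---|---|---|---|
| 8 | 0.0064 | 2.727 | cumulative | 2.8% | 2.51 | 61% | 69% |
| 8 | 0.0064 | 2.727 | cumulative, attrition | 3.5% | 2.59 | 61% | 66% |
| 12 | 0.0043 | 2.858 | cumulative | 2.4% | 2.58 | 56% | 66% |
| 12 | 0.0043 | 2.858 | cumulative, attrition | 3.0% | 2.67 | 56% | 63% |
| 15 | 0.0034 | 2.928 | cumulative | 2.2% | 2.62 | 53% | 65% |
| 15 | 0.0034 | 2.928 | cumulative, attrition | 2.7% | 2.70 | 53% | 62% |

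True family-wise error is thus 2.2-3.5%, and max-T gains about 5-12 points. With a correlation of 0.3 between all stages, max-T gains only about 1 point.

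**Holm-Šídák.** The ordered p-values are compared in turn with 1 − 0.95^(1/(K−j+1)), j = 1, …, K, stopping at the first failure. For K = 8 the limits begin at 0.0064 and 0.0073 and end at 0.05. The smallest is the single-step limit, so everything that single-step Šídák rejects is still rejected. With the cumulative structure and all stages shifted, power rises from 61% to 71% (K = 8), 56% to 66% (K = 12) and 53% to 64% (K = 15). Over correlations from 0.3 to 0.9 the gain is 8-12 points if all stages are shifted and about 3-4 if half are. The chance of at least one rejection does not change, because the first step is the same.

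**The case against.** The strongest reply is that nothing here is wrong. For two-sided tests on jointly normal statistics, Šídák's rule holds family-wise error at or below 5% whatever the correlation. It is a standard, cautious choice for a secondary objective on which the plan promises no power. That stands: this is an efficiency point.

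Four stronger readings are tempting, and the documents do not support them.

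- **That single-step was used as a matter of record.** It is the natural meaning of the unqualified name, but Section 8 does not say so. If a step-down version was used, only the max-T gain remains.
- **That true family-wise error is as low as 1.4%, with max-T gains well above 12 points.** That needs a correlation of 0.9 between every pair of stages. Cumulative times do not behave so: first and last stages correlate at 0.26-0.35 in the model above, and attrition lowers this further.
- **That Holm-Šídák repairs the loss due to correlation.** It does not use the correlation; it gains by relaxing the limit after each rejection. Only max-T uses the correlation. The 8-12 point gain also needs every stage shifted by the same 3.0 SE. Section 6 gives reason to doubt that, since the contrast with the 5% control changes from 8% to 2% oxygen around Day 3.
- **That the rule can simply be replaced.** The document is dated April 2025, after data collection, and describes the correction in the past tense. Moving to a more liberal rule after seeing results weakens credibility unless the change is labelled.

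The objection that max-T is not straightforward here also stands in part. Swapping arm labels within patient assumes that the quasi-random allocation, whose method is not described, is exchangeable. Some patients may have no late-stage embryos in one arm.

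**Conclusion.** The point holds as a loss of efficiency on a secondary objective. Single-step Šídák is valid for these timings but conservative. With 8-15 stages, correct standard errors, a 3.0 SE effect and cumulative-time correlation with or without attrition, its true family-wise error is about 2.2-3.5%. Holm-Šídák offers a modest gain with the same family-wise control; the size of the max-T gain depends on a correlation that the documents do not give.

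A reader might infer that the reported timing p-values are invalid or that the primary result is affected. Neither follows: error control is intact, and the day 5 blastocyst comparison and its sample size do not involve this correction. The correct-standard-error premise cannot be checked, because the random effects of the mixed model are not stated.

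**What to change.** In Section 8:

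1. List the stages that form the family. Without the list no Šídák threshold can be reproduced.
2. Name the variant, and replace single-step Šídák with step-down Holm-Šídák computed from the unadjusted mixed-model p-values. The adjusted value for the j-th smallest p-value is the maximum, over i ≤ j, of 1 − (1 − p_(i))^(K−i+1).
3. Optionally add a max-T analysis as a sensitivity analysis, with the reference distribution obtained by swapping arm labels within each patient. State the exchangeability assumption and how patients with no late-stage embryos in one arm are handled.
4. If results have already been seen, keep the Šídák result and report the step-down result beside it as a labelled sensitivity analysis.

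The cost is a short text change and a calculation on existing p-values; max-T also needs a short permutation program. No new data are required. The downsides are that the step-down version has no simple matching simultaneous confidence intervals, and that an unlabelled post hoc change of rule would reduce credibility.
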